	To monitor and compare quality-of-life (QoL) alterations during therapy courses.	
 – QoL: assessment undertaken at study enrolment, completion of the active therapy of the first treatment sequence (after 16 weeks), and disease progression, using the consensus modules EORTC QLQ-C30, EORTC QLQ-CIPN20, and EQ-5D-5L (http://groups.eortc.be/qol/, http://www.euroqol.org/).
Tertiary	To compare costs for the resource use (in diagnostic work-up, treatment, and any AE) for the sequential therapy with that of the standard-of-care, applying a model specifically developed for CRC.	
 – Cost estimate: model described in Joranger P et al., Med Decis Making 2015; 35, 256–65.
Exploratory	To develop circulating biomarkers of cytotoxic T lymphocyte activity.	
 – Surrogate measure of cytotoxic T lymphocyte activity: phosphatase activity in serial peripheral blood mononuclear cells (PBMC) samples, collected corresponding to each change of therapy (from FLOX to nivolumab and reverse) of the sequential regimen.
	To develop circulating biomarkers of tumor response.	
 – Surrogate response marker: alterations of circulating tumor DNA (ctDNA) and exosomal miRNA in plasma samples, collected corresponding to each change of therapy in the sequential regimen.
	To develop circulating biomarkers of ICD.	
 – Measures of circulating immune factors and T cell phenotypes in serial serum/plasma/whole blood samples collected corresponding to each change of therapy in the sequential regimen.
	To develop functional MR imaging biomarkers .	
 – TME responses in abdominal metastases: repeat functional MR imaging, undertaken corresponding to each change of therapy (from FLOX to nivolumab and reverse) during the first two months of the sequential regimen (three recordings in total), and correlate such changes with RECIST/iRECIST measures and PFS.

To develop histologic and molecular tumor biomarkers.

- Immune responses in liver/peritoneal metastases: histologic and molecular profiling in repeat liver/peritoneal biopsy samples collected corresponding to each change of therapy (from FLOX to nivolumab and reverse) during the first two months of the sequential regimen (three biopsy procedures in total), and correlate such changes with RECIST/iRECIST measures and PFS.

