Laboratory analyses ¹³	X	X ¹⁴	X ¹⁴	X ¹⁴	X ¹⁴	
Urine analysis ¹⁵	X	X ¹⁴	X ¹⁴	X ¹⁴	X ¹⁴	
Treatment administration						
FLOX						
Nivolumab						
Evaluation procedure(s)						
CT ¹⁷	X	X				
Correlative study procedures						
Whole blood sampling						
Plasma and serum sampling	X	X				
PBMC sampling ¹⁹	X	X				
Functional MR liver acquisition ^{19,20}						
Liver/peritoneal biopsy sampling ²¹						

- 1 Repeat after break period with disease progression, continue until progressive disease on ongoing therapy.
- 2 Until disease progression.
- 3 Analysis on primary or metastatic tumor.
- 4 Only at visit 2.
- 5 By completion of the active therapy of the first treatment sequence (after 16 weeks), *i.e.*, at first visit in first treatment break.
- 6 Until all study drug-related AE are resolved, have returned to baseline, or are deemed irreversible; reported for at least 100 days after last dose administration of IMP.
- 7 To be undertaken if clinically indicated from V1 onward, but mandatory at the 30 days safety follow-up visit.
- 8 May be omitted if full physical examination has been undertaken 14 days or less prior to the first dose of trial treatment.
- 9 For WOCBP.
- 10 Within 24 hours prior to the start of study drug.
- 11 Every 4 weeks.
- 12 Every 4 weeks; in the control arm, for 30 days after the last dose of study drug; in the experimental arm, for 160 days after the last dose of study drug.
- 13 Laboratory tests: Hb, HCT, WBC (including differential counting), platelets, liver factors (ALT, AST, ALP, LDH, GGT, total bilirubin, total albumin, INR), creatinine or urea, Na, K, Ca, Mg, phosphate, glucose, TSH, free T4, CEA, Ca19.9, Ca125.
- 14 Until all study drug-related abnormalities are resolved, have returned to baseline, or are deemed irreversible.
- 15 Dipstick.
- 16 FLOX in control treatment arm, nivolumab in experimental treatment arm.
- 17 In addition to computed tomography (CT) scan, MR scans or other radiologic evaluations will be performed if indicated.
- 18 Baseline CT scan must be taken within 28 days prior to the start of study drug.
- 19 Participation is optional for study centers.
- 20 Patient must not present contraindication to the procedure. Procedure must be done before a metastatic lesion in the liver/peritoneum is sampled.
- 21 Baseline sampling is mandatory; follow-up sampling is optional.

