7.10.5 Repeat collection of metastatic tissue

Experimental arm patients will undergo repeat sampling of core biopsies from liver/peritoneal metastases at time points corresponding to each change of therapy (from FLOX to nivolumab and reverse) during the first two months of the sequential regimen (*i.e.*, three sampling procedures in total; one or both of the resampling procedures, *i.e.*, others than that at baseline, are excused if the total number of three procedures is not feasible). Control arm patients will undergo biopsy sampling at baseline and may also be exempt from repeat sampling at the discretion of Clinical Investigator. For an individual patient, repeat sampling will preferentially be from the same lesion every time. The sampling procedure will be ultrasound-guided. Ideally, to ensure that the material from the sampling locus is representative, a regular smear from a fine-needle aspirate will be assessed by a pathologist at site. Next, 1–3 core biopsies will be taken and tumor cell content estimated by tissue imprint prior to freezing in liquid nitrogen [[name] *et al.*, 2017]. The samples will be dispatched to the study biobank at Akershus University Hospital upon request. Please refer to the specified SOP document (in Investigator Site File).

The 1–3 biopsy samples will be utilized in the following priority: 1) histology/immune histochemistry, 2) RNA applications, and 3) DNA applications. Specifically, the total number of T cells (CD3-positive) will be determined, with identification of T cell subpopulations by their expression of specific proteins (CD8-positive cytotoxic and FoxP3-positive regulatory T cells), as recently shown in a pilot study (Dagenborg *et al.*, manuscript in preparation). Also, CRC liver metastasis samples were recently analyzed by gene expression microarrays and indicated immune activity profiles in patients who had received neoadjuvant FLOX [Østrup *et al.*, 2017]. Comprehensive gene mutation analysis will be done [[name] *et al.*, 2017]. Of note, a number of RNA-based methods will be applied to specifically investigate novel mechanisms of anti-tumor immunity. Also, tumor PD-L1 expression, consensus molecular subtype, and mutation burden may be determined.

Participation in the histologic and molecular investigational sub-studies is mandatory (baseline biopsy sampling; follow-up biopsy sampling is optional) for study centers.

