8.1 Definitions

An AE is defined as any new untoward medical occurrence or worsening of a preexisting medical condition in a subject administered a study drug and which does not necessarily have a causal relationship with this treatment. An AE can therefore be any unfavorable and unintended sign (including an abnormal laboratory finding), symptom, or disease temporally associated with the use of a medicinal (investigational) product, whether or not cautiously related to the medicinal (investigational) product.

The causal relationship to a study drug is determined by a physician and can be one of the following:

- Related: There is a reasonable causal relationship between study drug administration and the AE.
- Not related: There is not a reasonable causal relationship between study drug administration and the AE.

The term “reasonable causal relationship” means there is evidence to suggest a causal relationship. AE can be spontaneously reported or elicited during open-ended questioning, examination, or evaluation of a subject.

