8.2 SAE (serious adverse events) collection and reporting

For nivolumab, the IB represents the reference safety information to determine expectedness of SAE for expedited reporting. For the FLOX regimen, the SmPC of each of the drug components represents the reference safety information. Following the subject's written consent to participate in the study, all SAE (in both study arms), whether related or not related to study drug, must be collected, including those thought to be associated with protocol-specified procedures. All SAE must be collected that occur during the screening period and within 100 days of the last dose of nivolumab. If applicable, SAE must be collected that relate to any later protocol-specified procedure.

Clinical Investigator must report any SAE that occurs after these time periods and that is believed to be related to any IMP or protocol-specified procedure, pertaining to the full duration of the study (c.f., Paragraph 7.8), which is in accordance with European Commission guidelines.

An SAE report must be completed for any event where doubt exists regarding its seriousness.

If Clinical Investigator believes that an SAE is not related to study drug, but is potentially related to the conditions of the study (such as withdrawal of previous therapy or a complication of a study procedure), the relationship must be specified in the narrative section of the SAE report form.

SAE, whether related or not related to study drug, and pregnancies, must be reported to Sponsor (or designee) within 24 hours of awareness of the event. SAE will be recorded on the Suspect Adverse Reaction Report form by the Council for International Organizations of Medical Sciences (CIOMS), c.f. Appendix 10. Pregnancies will be recorded on a Pregnancy Surveillance Form.

If only limited information is initially available, follow-up reports are required. All SAE must be followed to resolution or stabilization.

If an ongoing SAE changes in its intensity or relationship to study drug or if new information becomes available, the SAE report must be updated and submitted within 24 hours to Sponsor (or designee) using the same procedure used for transmitting the initial SAE report.

Sponsor's representative for SAE notifications has the following address:

[contact]

and

Cell Phone: ([contact]

Sponsor will immediately forward SAE notifications (in experimental arm patients) to the following address:

[contact]

or

Facsimile Number: (+1) [contact]

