#### 5.2. Analysis methods

*Main statistical analyses.* The main statistical analysis is planned after the last patient has fulfilled the pre-defined follow-up period. PFS will be calculated from the day of randomization to first recorded disease progression according to RECIST v1.1 or when applicable iRECIST, or death. Patients who have not had disease progression at the time of final analysis will be censored at the date last known to be alive and progression-free. The analyses will compare the treatment groups in total as well as groups stratified by primary tumor sidedness and (K)RAS/BRAF mutation status.

*Interim analyses.* Interim analyses will apply to data on safety, tolerability, possible detrimental effects, and curative outcomes, and will be based on purely clinical judgment by the External Data and Safety Monitoring Committee. These types of data will be reported as the number of events.

*Descriptive statistics.* Demographic and clinical characteristics will be presented as means and standard deviations, medians with minimum and maximum values, or frequencies and percentages, as appropriate. Further statistical analyses will be separated to primary analyses, including only comparison of primary end point between two treatment arms, and secondary analyses, including stratified analyses on primary and secondary end points as well as number of analyses on secondary end points.

*Primary analysis.* Median PFS time will be compared between study arms by drawing Kaplan-Meier survival curves and performing log-rank test. HR with the corresponding 95% CI and p-values will be estimated by Cox proportional hazards model.

*Secondary analyses.* Distribution of PFS times stratified by the primary tumor sidedness and (K)RAS/BRAF mutation status will be illustrated graphically by Kaplan-Meier curves and compared by log-rank test. To assess the hazard rates for disease progression within each strata, Cox proportional hazards model will be estimated and, if appropriate, adjusted for relevant covariates. The results will be presented as HR with the corresponding 95% CI and p-values.

Safety. The number of serious adverse events (SAE) will be summarized and presented by trial arm. In addition, information will be given on the number of SAE per participant, together with details on the causality, expectedness, and outcome of each SAE experienced. Summaries of suspected unexpected serious adverse reaction (SUSAR) events will also be presented by trial arm.

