Tolerability. Summaries by trial arm will be produced to show the proportion of participants experiencing each grade of CTCAE toxicities overall and during each treatment cycle. For more detailed summaries, this information will also be broken down into the different types of toxicities.

QoL. This will be summarized for each treatment arm at study enrolment, completion of the active therapy of the first treatment sequence (after 16 weeks), and disease progression, using the consensus modules EORTC QLQ-C30, EORTC QLQ-CIPN20, and EQ-5D-5L. The data will be illustrated graphically and presented as mean scores with 95% CI at separate time points. The differences in QoL between two treatment arms throughout the study period will be assessed by estimating a linear mixed model with fixed effects for time and treatment arm and the interaction between these two. Random effects for patients will be included. A significant interaction will quantify differences between the groups and serve as an omnibus test.

Safety and tolerability in the treatment arms will be compared by  $\chi^2$  or Fisher's exact test, as appropriate.

ORR is defined as the percentage of patients with a confirmed CR or PR. The proportion of participants achieving at least PR will be summarized with corresponding 95% CI for each treatment arm. The difference between the trial arms in the proportion of participants achieving at least PR will also be presented with corresponding 95% CI. The difference between participants achieving at least PR and remaining participants will be assessed using logistic regression adjusting for treatment group and stratification factors. Odds ratios with corresponding 95% CI and p-values will be presented for all variables incorporated in the model.

SSCRR is defined as the percentage of patients with a confirmed resection of metastatic disease with microscopically free margin (R0). Corresponding analyses as those to be performed for ORR will be applied for SSCRR.

DOR is defined as the time from the first documentation of CR/iCR or PR/iPR to disease progression. DOR Kaplan-Meier curves will be drawn and compared by log-rank test. The median DOR with corresponding 95% CI will be presented by treatment group. Stratified analyses will be performed as well. The Cox proportional hazards model, adjusting for the stratification factors, will also be used to compare DOR

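### Repeat research biopsies are scheduled mainly in the experimental arm and their complications are not kept out of the between-arm safety test, so equal drug toxicity can look somewhat worse there; the effect is probably small and cheap to separate out.

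*Protocol*

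**What the plan says.** **Biopsy schedule.** Protocol section 2 (exploratory objectives) places the experimental-arm biopsies at each change of therapy "during the first two months of the sequential regimen (three biopsy procedures in total"). The flow chart in section 6 marks biopsies at the screening visit and at cycles 3 and 5, that is, about weeks 4 and 8. For the other arm, section 7.10.5 states: "Control arm patients will undergo biopsy sampling at baseline and may also be exempt from repeat sampling at the discretion of Clinical Investigator". Both arms have some freedom to omit repeats. In the experimental arm one or both "are excused if the total number of three procedures is not feasible", and flow chart footnote 21 says for all patients: "Baseline sampling is mandatory; follow-up sampling is optional".

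**What counts as an event.** Protocol 8.1 defines an adverse event as an occurrence "which does not necessarily have a causal relationship with this treatment". Under 8.2 all SAE in both arms "must be collected, including those thought to be associated with protocol-specified procedures", starting from consent. Under 8.1.1 collection of non-serious events starts with the first study drug.

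**What is tested.** SAP 5.2 states: "The number of serious adverse events (SAE) will be summarized and presented by trial arm". It adds: "Safety and tolerability in the treatment arms will be compared by" a chi-square or Fisher's exact test. Protocol 10.4.5 says the same. Neither restricts the test by cause. Protocol section 3 and SAP 2.1 name superiority in safety and tolerability among the aims.

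**The concern.** The repeat biopsies serve an exploratory objective and belong to neither treatment regimen. One arm is scheduled for them, and the other may be spared them at the investigator's discretion. The protocol itself treats biopsy complications as real: section 12.2 requires the consent form to address them.

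For non-serious events the contrast is sharper than the schedule suggests. The baseline biopsy, the only one a control patient must have, precedes the collection window, whereas both repeats fall within it.

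A complication of a repeat biopsy is therefore an adverse event that enters the arm comparison and that the control arm has less opportunity to generate. Any resulting bias runs against the sequential therapy and says nothing about nivolumab or FLOX. At stake is the reading of a secondary comparison that the trial names among its aims. PFS and its sample size are not affected.

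**Working it through.** **Plan's own figure.** The documents give no rate or power for safety. The only calculated design figure is 40 patients per arm for PFS before adjustment. It reproduces with Freedman's formula: events = (1.96 + 0.84)² × [(1 + 0.5)/(1 − 0.5)]² ≈ 7.85 × 9 = 70.6, so 71. Then 71/0.9 = 78.9 in total, or 40 per arm. The adjusted 50 per arm is used below.

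**Inputs from the documents.** 50 patients per arm; 5% significance level (SAP 3.1), taken as two-sided; chi-square or Fisher's exact test; up to two repeat biopsies in the experimental arm inside the collection window; no obligatory repeats in the control arm.

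**Assumptions, because the documents are silent.** Risk r of a recorded complication per biopsy: 1%, 3% or 5%. Equal drug-related risk b in both arms: 20%. Independence of the two. No control repeats. Uptake u of both repeats in the experimental arm: half or all patients.

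**Step 1, extra procedures.** At most 2 × 50 = 100 in the experimental arm; at half uptake, 50.

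**Step 2, probability of at least one complication from two repeats.** x = 1 − (1 − r)². For r = 1%, 3%, 5%: x = 2.0%, 5.9%, 9.8%.

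**Step 3, observed experimental risk.** pE = b + (1 − b) × u × x, against pC = b = 20%. Newly affected patients = 50 × (pE − pC). At full uptake and r = 3%: pE = 0.20 + 0.80 × 0.059 = 24.7%, which is 2.4 patients. Using 50 × x instead would give 3.0, but that also counts patients who already have another event.

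**Step 4, chance of a significant result with the experimental arm worse.** Sum the exact binomial probabilities over all pairs of counts that the test rejects in that direction. With no biopsy events this is 2.6% by chi-square and 1.4% by Fisher.

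| r per biopsy | Uptake | Newly affected of 50 | Chi-square | Fisher |
|---|---|---|---|---|
| 1% | half | 0.4 | 3.2% | 1.8% |
| 1% | full | 0.8 | 4.0% | 2.3% |
| 3% | half | 1.2 | 4.8% | 2.9% |
| 3% | full | 2.4 | 8.2% | 5.3% |
| 5% | half | 2.0 | 6.9% | 4.3% |
| 5% | full | 3.9 | 14.8% | 10.4% |

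**Step 5, sensitivity.**
- If a quarter of control patients also have both repeats, against half of experimental patients, the chi-square figures are 2.9%, 3.5% and 4.3% for r = 1%, 3% and 5%.
- If b is 40%, full uptake gives 3.5%, 5.8% and 9.1%.
- For SAE, collected from consent, the baseline biopsy counts in both arms, so the contrast is three against one. At b = 20% and full uptake this gives 3.9%, 7.7% and 12.9% by chi-square, close to the table.

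**The case against.** The strongest reply has four parts.

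**Repeats are not obligatory in either arm.** This stands. Full uptake in one arm and none in the other is the extreme the text allows, not what it predicts. Control patients may also have repeats.

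**Recording is narrow.** SAP 5.5 limits recording to grade 3–5, apart from grade 2 immune-related hepatotoxicity, and protocol 8.1.2 does not count a planned procedure admission as an SAE. This also stands and favours the lower values of r.

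**Cause is not ignored.** Causality is given for each SAE, SAP 5.5 reports safety data by causality, protocol 8.2 asks for a study-procedure link in the SAE narrative, and toxicities are broken down by type and cycle. These provisions help a reader recognise a biopsy event, but they do not change what is tested. The narrative is free text and covers SAE only. The CRF scale in protocol 8.9 grades relation to the IMP, so a non-serious grade 3 biopsy event would at best be marked unrelated, without saying to what it was related.

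**Filtering by attribution has its own bias.** Attribution is open-label, and some events, such as bleeding with low platelets or a liver-enzyme rise on nivolumab, cannot be cleanly assigned to needle or drug. This stands and is the reason not to replace the all-cause test.

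Three stronger readings are tempting:
- A reader might infer that equal drug toxicity will show up as excess harm. That needs about 5% or more recorded complications per biopsy together with near-full uptake in one arm only, and the documents support neither.
- A reader might infer a large loss of power to show a safety benefit. For an assumed 20% against 40%, chi-square power of 60% falls to 48% at r = 3% with half uptake and 37% with full uptake. Those toxicity rates appear nowhere in the documents.
- A reader might infer that the cost comparison is inflated too. Protocol section 2 includes costs of any adverse event, but SAP 5.1 describes the costs as those of sequencing procedures and administered medication. Whether biopsy complications enter cannot be settled from the text.

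**Conclusion.** The structural point holds. The experimental arm is scheduled for up to two more research biopsies than the control arm must have, both inside the collection window, and no rule keeps their complications out of the between-arm test. Any bias goes one way, against the sequential therapy.

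Its size is uncertain and probably small. With 1–3% recorded complications per biopsy, 20% toxicity in both arms and no control repeats, about 0.4 to 2.4 of 50 patients gain an event. The false-worse rate goes from 2.6% to about 3–8% by chi-square, or from 1.4% to about 2–5% by Fisher, across half to full uptake. The complication rate, base toxicity and uptake are all assumptions.

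The comparison affected is secondary and unadjusted for multiplicity. Low severity: a cheap improvement, not a flaw that undermines the trial.

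**What to change.** 1. Add one item to each AE and SAE record in the CRF: related to a research biopsy or study MR, yes or no, completed at the time of the event.
2. Keep the all-cause between-arm test in SAP 5.2 and protocol 10.4.5 as the reference.
3. In the same two sections, pre-specify a supplementary between-arm comparison that leaves out events attributed to research-only procedures.
4. Add a separate table of procedure-related events by arm, with the number of biopsies performed in each arm as denominator. The biopsy counts alone will show how much imbalance actually arose.

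Cost: one tick-box and a few lines of SAP and protocol text, with no extra patients, visits or procedures. The downside is that attribution is made open-label, so the supplementary result should be read beside the all-cause result and not in place of it.
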